Clients to be included in the Aim 1 secondary analyses of the stepped-wedge trial of D2S will be identified through the analysis of merged programmatic (eSHARE) and surveillance (NYC HIV Registry) data, based on the eligibility criteria noted above (concerning enrollment status/timing, vital status and viral suppression [VS] status in a given reporting period). Additional data elements from the NYC HCV Registry will be incorporated into Aim 1 secondary analyses without the modification of existing inclusion/exclusion criteria. Clients to be included in Aim 2 secondary analyses of drivers of VS will represent a subset of clients analyzed for Aim 1 – specifically, those clients who were exposed to the D2S intervention during the course of the trial.

For Aim 3, recruitment for the focus groups is as follows: Primary data collection will include five focus groups with an average of nine providers each (N ≈ 45) and three additional focus groups with an average of nine clients each (N ≈ 27). Provider groups will be organized by setting (clinical versus non-clinical/CBO), and split within setting by program role: administrative (including information-technology/data managers and program directors or medical directors),

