To utilize repeated observations from clients eligible in two or three periods, the exact, conditional analysis will be prepared under the assumption of conditional independence of TVS outcomes, not unlike assumptions typically used in mixed-model analysis. In this case, the analysis is valid if the conditional distribution of the number of TVS events in Site 1 of a given pair in a given time period does not depend on the corresponding number of TVS events for Site 1 in prior periods. Insofar as many new clients are introduced in successive periods and insofar as opportunities for TVS may depend only on the site, period, and intervention effect, not on past TVS failures, the conditional independence assumption is tenable. Note that such conditional independence does not preclude marginal correlations over time

for individual clients. As a sensitivity analysis, we will re-estimate the intervention effect omitting repeated observations to confirm there are no material changes.

HCV Cure Analysis Plan. In an added secondary analysis, the effect of exposure to D2S reports on HCV cure will be measured by comparing HCV treatment receipt and cure status among clients with HCV coinfection at agencies that received D2S reports with HCV treatment receipt and cure status among clients at agencies that did not receive HCV reports. HCV treatment receipt will be defined as a client's first negative HCV RNA Qualitative NAA test preceded by a positive RNA test. HCV cure will be defined as two consecutive negative HCV RNA tests any time after the most recent positive HCV RNA test. A 12-week buffer period (after report dissemination) will be applied to avoid attributing to the reports HCV cures resulting from HCV treatment initiated prior to report distribution. The 12-week buffer period applies if the 2nd negative RNA test was within the 12 weeks after reports were disseminated. This analysis will include data from individuals in Period 0 and Period 1. Similar statistical methods as described above will be used to examine the effect of agencies' exposure to D2S reports on HCV cure among PWH with an HCV coinfection. Difference-in-Difference (DID) estimation may also be incorporated to estimate the effect of D2S report exposure on the outcome by comparing changes in the outcome over time (Period 0 to Period 1).

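### The added HCV analysis reads both outcomes from RNA results alone: 'treatment receipt' is only a proxy for treatment, and 'cure' can rest on two closely spaced negatives

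*Combined protocol and SAP*

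**What the plan says.** Section K, Aim 1, HCV Cure Analysis Plan, introduces the comparison: "In an added secondary analysis, the effect of exposure to D2S reports on HCV cure will be measured by comparing HCV treatment receipt and cure". The contrast is between agencies with and without reports. The two outcomes are defined as follows.

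- Treatment receipt: "HCV treatment receipt will be defined as a client's first negative HCV RNA Qualitative NAA test preceded by a positive RNA test".
- Cure: "HCV cure will be defined as two consecutive negative HCV RNA tests any time after the most recent positive HCV RNA test".

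The only timing rule is a buffer. Its purpose is attribution: "A 12-week buffer period (after report dissemination) will be applied to avoid attributing to the reports HCV cures resulting from HCV treatment initiated prior". The quoted sentence goes on to name distribution of the reports as the reference point. The trigger is the date of one test: "The 12-week buffer period applies if the 2nd negative RNA test was within the 12 weeks after reports were disseminated". No buffer is stated for treatment receipt.

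On data, section G says: "Additional data elements from the NYC HCV Registry will be incorporated into Aim 1 secondary analyses without the modification of existing inclusion/exclusion criteria". No prescription, claims or other treatment record is mentioned. On periods: "This analysis will include data from individuals in Period 0 and Period 1". On method, the sentence names cure only: "Similar statistical methods as described above will be used to examine the effect of agencies' exposure to D2S reports on HCV cure". Difference-in-difference estimation is optional.

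**The concern.** An outcome called treatment receipt should record that treatment began. Here it records a laboratory result. A treated client with no negative on file counts as untreated, and a client whose RNA becomes negative without treatment counts as treated. Both outcomes also need a test to have been done, so both depend on how often clients are tested. Testing happens after randomization, so randomization does not balance it.

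Cure has a related weakness. With no minimum interval and no link to the course of treatment, a repeat sample a day after the first negative completes the definition, although nothing new has been learned about a lasting response.

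At stake is the wording of the HCV conclusion. A difference between arms could be reported as more treatment or more cure when part of it, or all of it, reflects clearance without treatment or more frequent testing.

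**Working it through.** **Inputs.** The two definitions and the buffer come from the HCV Cure Analysis Plan; 12 weeks is 84 days. The documents give no HCV sample size, event count, retesting rate, effect size or power (the trial power figures in section K concern viral suppression). There is thus no HCV figure to reproduce, and every rate in steps 2 and 3 is an assumption.

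**Step 1: apply the cure rule to hypothetical test dates.** The report is on day 0. A cure counts if two negatives follow the last positive and the second does not fall in days 0 to 84. This reads the buffer as not counting such cures. The last positive is on day −30, or day −70 in the fourth row.

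| Treatment start | Negatives on days | Gap (days) | Rule as written | With an 84-day minimum gap |
|---|---|---|---|---|
| Day 60 | 88 and 89 | 1 | Cure, 29 days after start | Not cure |
| Day 60 | 88 and 116 | 28 | Cure, 56 days after start | Not cure |
| Any | 40 and 80 | 40 | Not counted (buffer) | Not counted |
| Day −60 | −10 and 90 | 100 | Cure | Cure |

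The documents state no length of treatment. The first row is a cure counted during treatment if the course runs longer than 29 days, and the second if it runs longer than 56 days. The buffer misses both because it looks only at the second negative's distance from the report. The fourth row shows that a minimum gap does not settle attribution.

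**Step 2: the proxy when errors are equal in both arms.** Let *t* be the true treated share, *a* the probability of a recorded negative if treated, and *b* the same if untreated. Then observed share = *t·a* + (1 − *t*)·*b*. Take *t* = 0.30 in control and 0.45 with D2S. The true odds ratio is (0.45/0.55)/(0.30/0.70) = 1.91.

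| *a* | *b* | Control | D2S | Observed odds ratio |
|---|---|---|---|---|
| 0.90 | 0.05 | 0.305 | 0.4325 | 1.74 |
| 0.80 | 0.10 | 0.310 | 0.415 | 1.58 |
| 0.60 | 0.10 | 0.250 | 0.325 | 1.44 |
| 0.60 | 0.20 | 0.320 | 0.380 | 1.30 |

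First row: 0.30 × 0.90 + 0.70 × 0.05 = 0.305, and 0.45 × 0.90 + 0.55 × 0.05 = 0.4325. The effect shrinks but remains.

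**Step 3: the proxy when only retesting differs.** Assume the same treated share (0.30) in both arms, and among retested clients a negative in 0.95 of the treated and 0.05 of the untreated. Observed share = retested share × (0.30 × 0.95 + 0.70 × 0.05) = retested share × 0.32. With 60% retested in control this is 0.192.

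- D2S retesting 60%: 0.192, odds ratio 1.00.
- D2S retesting 70%: 0.224, odds ratio (0.224/0.776)/(0.192/0.808) = 1.21.
- D2S retesting 80%: 0.256, odds ratio (0.256/0.744)/(0.192/0.808) = 1.45.

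The direction here is an input. If D2S agencies tested less, the odds ratio would fall below 1.

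**The case against.** Several points on the other side are sound.

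- A reader might infer that the analysis cannot show any effect on treatment. Step 2 does not support that: with equal error in both arms, the effect is diluted but can still be detected.
- A reader might say the cure rule ignores relapse. It does so only in part. Cure is anchored to the most recent positive, so a recorded later positive cancels an earlier pair. Only a relapse not yet retested escapes.
- A reader might call the two outcomes one event counted once or twice. They overlap heavily, but a positive–negative–positive sequence is receipt without cure, so they can diverge.
- A reader might see the buffer as contradicting the cure rule. It does not. The buffer decides whether a cure may be credited to a report, and the cure rule decides what a cure is. The buffer simply leaves the spacing of tests open.
- A reader might expect the bias to favour D2S. Section P says that listed clients may receive faster follow-up, which makes more testing plausible. But section J, Aim 1, describes reports built on HIV viral load, vital status and program activity, and nothing says that they prompt HCV RNA testing.

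It is also fair that a laboratory proxy may be all the Registry allows, and that the effect and method sentences are directed at cure. What remains is that the first outcome carries a name its definition does not support, and that the cure definition accepts pairs of any spacing.

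**Conclusion.** The point holds as a matter of definition. Followed as written, the plan would report a rise in clearance or retesting as treatment receipt, and would count two closely spaced negatives, including ones taken during treatment, as cure. A difference in the first outcome cannot be attributed to treatment uptake alone.

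No size or direction can be given for this trial. The figures of 1.30 to 1.74 (against a true 1.91) and of 1.21 and 1.45 (against a true 1.00) rest wholly on assumed rates and show only how the proxy behaves. That the definitions allow early pairs needs no assumed rate; that such a pair falls during treatment depends on a course length the documents do not give.

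The scope is an added secondary analysis. The primary TVS test uses HIV viral load and is untouched. This is a cheap improvement to make before the HCV data are analysed.

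**What to change.** These changes concern analysis definitions only, not how clients are tested or treated.

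1. Label the first outcome *first HCV RNA clearance (proxy for treatment)* and do not attribute a difference in it to treatment uptake alone.
2. Keep the cure definition, including its anchor to the most recent positive, and add a pre-specified minimum interval between the two negatives. The plan's 12-week figure is one candidate, but it was set for attribution, so the sponsor should justify the choice. The wording should allow further negatives in between. Otherwise a client tested every 42 days would never have adjacent negatives 84 days apart. Report the any-gap definition as a sensitivity analysis.
3. Report HCV RNA test frequency by arm and period. The minimum interval removes early pairs, but a second test is still needed, so dependence on testing remains. Nor does the interval, counted from the first negative, prove that the second sample was taken after treatment ended.

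The changes need plan wording, some programming and the same Registry data. The cost is fewer cure events, because some clients will have no sufficiently late second test. The loss falls most on those whose first negative comes late.

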Retrospective Analyses to Generate Estimates for Power Calculations. A retrospective analysis of data from the behavioral health and housing programs at the 27 selected agencies was conducted to review the TVS outcome among clients unsuppressed as of last VL test in July 2016 – June 2017 (a mock “Round 1, Period 0” report lookback period), and for additional clients (i.e., clients not flagged in Round 1) who were unsuppressed as of last VL test in January – December 2017 (a mock “Round 2, Period 0” report lookback period). The same process was used to generate simulated data for two rounds of reports (covering July 2017 – June 2018 and January – December 2018) for a mock “Period 1” at those agencies, and two rounds of reports (covering July 2018 – June 2019 and January – December 2019) for a mock “Period 2” at the same agencies. Clients found to have a suppressed VL dated after their qualifying unsuppressed VL but prior to the time when a D2S report could have been issued (two months following the end of the 12-month reporting lookback period) were excluded from the eligible N for follow-up from that simulated report, since they could not be evaluated for timely achievement of suppression following the date of report issue. The remaining eligible clients within each simulated period were followed for VS (any VL <200 copies/mL) within the six-month period starting exactly two months after the end of the report year in which they were flagged as unsuppressed. Through this method, we arrived at (1) an estimate of 1,283 unique unsuppressed people with HIV (PWH) to be included in the trial, and (2) an estimate of 43.7% TVS in the pre-intervention base case. The N to be included in analyses of time to VS is smaller due to the longer (12-month) follow-up time and the start of each implementation period exactly 12 months after the start of the prior implementation period. To allow a full, discrete 12-month follow-up period, while avoiding contamination between intervention and control observations, the time to VS outcome will only be measured among clients flagged as unsuppressed in reports issued at the start of each period (“Round 1” reports). This does not cut the N in half, because Round 1 reports include more clients newly flagged as unsuppressed, as compared with Round 2 reports, and clients unsuppressed at both rounds (duplicated clients) within an implementation period are not eligible for follow-up for Round 2, for either outcome measure.

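### The added HCV analysis sets no RNA-positive risk set at report issue and no closing date, so old cures dilute the contrast and some cures reached under D2S are credited to control

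*Combined protocol and SAP*

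**What the plan says.** The HCV Cure Analysis Plan (section K, Aim 1) compares HCV treatment receipt and cure between agencies that did and did not receive reports.

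- **Cure:** "HCV cure will be defined as two consecutive negative HCV RNA tests any time after the most recent positive HCV RNA test".
- **Treatment receipt:** the client's "first negative HCV RNA Qualitative NAA test preceded by a positive RNA test". No window is given here either.
- **Buffer:** a 12-week period is meant "to avoid attributing to the reports HCV cures resulting from HCV treatment initiated prior to report distribution". Its operating rule is: "The 12-week buffer period applies if the 2nd negative RNA test was within the 12 weeks after reports were disseminated".
- **Data:** "This analysis will include data from individuals in Period 0 and Period 1".
- **Method:** "Similar statistical methods as described above will be used to examine the effect of agencies' exposure to D2S reports on HCV cure", with difference-in-differences (DID) from Period 0 to Period 1 as an option.
- **Eligibility:** section G says that the HCV Registry elements "will be incorporated into Aim 1 secondary analyses without the modification of existing inclusion/exclusion criteria". Those criteria concern programme enrolment, vital status and HIV suppression. HCV coinfection is not defined by date or by RNA status.

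The HIV outcomes are handled differently. Under Retrospective Analyses to Generate Estimates for Power Calculations (section K), clients already suppressed before a report could issue are removed. Timely viral suppression (TVS) has a fixed six-month window. Time to suppression uses Round 1 reports only, for this reason: "To allow a full, discrete 12-month follow-up period, while avoiding contamination between intervention and control observations".

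Section J (Aim 1) gives D2S to 13 agencies in Period 1 and to all 27 in Period 2.

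**The concern.** The HCV outcome lacks both guards that the HIV outcomes have.

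**No start.** A client whose two negatives predate the report meets the cure definition. If eligible in both periods, that client can count as cured twice. The buffer acts on a second negative within 12 weeks after dissemination, so a cure completed before dissemination falls outside its rule.

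**No end.** An early agency's Period 0 client can be cured during Period 1, when that agency has D2S, and still be counted in a control cell. If follow-up continues into Period 2, the same holds for Period 1 clients at delayed agencies.

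The analysis would then mix cures that precede the reports, cures under usual care and cures under D2S. A null or weak HCV result would be hard to interpret.

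Carrying cure status forward also sits badly with the exact conditional method. The Viral Suppression Analysis Plan makes its validity depend on one period's event count not depending on the counts of earlier periods at that site.

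**Working it through.** The plan gives no HCV sample size, cure rate, effect size or power, so there is no HCV figure to reproduce. What follows is an illustration.

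**Assumed inputs.** Cure per 12-month period is 10% without D2S and 20% with it. The true OR is (0.20/0.80)/(0.10/0.90) = 2.25. Prior-cure shares are equal across sites, there is no secular trend, and follow-up runs in whole years.

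**1. Old cures only, closed window.** With a share c already cured at report issue, the observed proportion is p = c + (1 − c)h, where h is the 12-month cure probability.

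| c | Control p | D2S p | OR |
|---|---|---|---|
| 0.20 | 0.28 | 0.36 | 1.45 |
| 0.40 | 0.46 | 0.52 | 1.27 |
| 0.60 | 0.64 | 0.68 | 1.20 |

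Old cures enter D2S and control cells alike. They dilute the contrast without removing it.

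**2. Cross-over only (c = 0).** Cumulative cure is one minus the product of (1 − h) over the years each cell is followed.

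| Cell | Closed window | Cut at end of Period 1 | Cut at end of Period 2 |
|---|---|---|---|
| Early, Period 0 | 0.10 | 1 − 0.9×0.8 = 0.28 | 1 − 0.9×0.8×0.8 = 0.424 |
| Early, Period 1 | 0.20 | 0.20 | 1 − 0.8×0.8 = 0.36 |
| Delayed, Period 0 | 0.10 | 1 − 0.9×0.9 = 0.19 | 1 − 0.9×0.9×0.8 = 0.352 |
| Delayed, Period 1 | 0.10 | 0.10 | 1 − 0.9×0.8 = 0.28 |
| Ratio of ORs | 2.25 | 1.36 | 1.07 |
| DID | +0.10 | +0.01 | +0.008 |

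The ratio of ORs is the early agencies' Period 1/Period 0 odds ratio divided by that of the delayed agencies. For the cut at the end of Period 1 it is (0.2500/0.3889)/(0.1111/0.2346) = 1.36.

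That figure has all Period 0 clients staying active. If half leave and continue at the 10% rate, the early Period 0 cell is 0.5×0.28 + 0.5×0.19 = 0.235 and the ratio is 1.72.

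**3. Other rates.**
- 5% against 10% (true OR 2.11) gives 1.34 and 1.07 at the two cuts.
- 20% against 35% (true OR 2.15) gives 1.31 and 1.06.
- Borrowing the TVS power target (OR 1.86) with control cure of 10% to 30% gives 1.24–1.28 and 1.05–1.06. A closed window with an RNA-positive risk set returns 1.86.

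**4. Both together.** With c = 0.40 and a cut at the end of Period 1, the cells in table order are 0.568, 0.52, 0.514 and 0.46. The ratio is (1.0833/1.3148)/(0.8519/1.0576) = 1.02.

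**5. Period 1 only, early against delayed (c = 0).** The OR stays at 2.25 with a cut at the end of Period 1. With a cut at the end of Period 2 it is (0.36/0.64)/(0.28/0.72) = 1.45.

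**The case against.** Four arguments on the other side deserve weight.

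- **The Period 0 and Period 1 sentence may imply a cut-off.** DID from Period 0 to Period 1 also suggests an outcome measured within each period. This is a fair reading, and under it delayed agencies' Period 1 cells take in no D2S-era cures. The sentence selects individuals, however, and does not date outcomes. Even with that cut-off, the early agencies' Period 0 cell still collects Period 1 cures.
- **The restriction to coinfected clients may exclude people cured long ago.** It may, but the term is undefined, and the cure definition asks only for a past positive followed by two negatives.
- **The buffer's purpose covers earlier-treated cures.** That shows intent. The operating rule does not deliver it, and the plan does not say how the buffer runs in control cells, where no report was disseminated.
- **All the rates are assumed.** This stands. The direction also rests on comparable prior-cure shares across sites and no secular trend.

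A reader might go further and infer that the contrast is erased, or that a real benefit would be reported as none. The documents do not support that. Old cures alone only dilute. Cross-over alone comes close to removing the two-period contrast only if follow-up runs through Period 2. A Period 1-only comparison is less affected, and without an HCV sample size nobody can say what would be reported.

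Nor are Period 0 clients always followed at least a year longer. With two rounds per period six months apart, a Period 0 Round 2 client precedes a Period 1 Round 1 client by about six months.

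**Conclusion.** The concern holds as a defect in the definition of an added secondary analysis. As written, pre-report cures count in all cells, and some cures reached under D2S count as control.

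Under the assumed rates, with comparable prior-cure shares across sites, the bias is toward the null. From cross-over alone it is partial with a cut at the end of Period 1 (about 1.36 against 2.25 if all Period 0 clients stay active) and almost complete with a cut at the end of Period 2 (about 1.07). Prior cures would add to this by an amount that depends on their unknown share.

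The sizes are illustrative, because the documents give no HCV rates. The absence of a risk set and a closing date is a matter of text and rests on no assumption. The primary TVS analysis is not affected. The wording should be corrected before the HCV analysis is run.

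**What to change.** Amend the HCV Cure Analysis Plan as follows.

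1. For each report round, fix an index date: the actual issue date in D2S cells and the nominal issue date in control cells.
2. Restrict the risk set to clients whose last HCV RNA on or before that date is positive.
3. Count treatment receipt and cure only from negatives drawn after that date, within a fixed window of the same length in all cells for that round, ending before the next period starts.
4. Apply the 12-week buffer identically in D2S and control cells, measured from the index date.
5. Count a client once per period. Remove the client from later risk sets once cured, unless RNA-positive again.

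The change is to wording and uses the same Registry data. It costs analysable clients, and cures confirmed after the window closes are not counted. Round 2 clients have less time before the next period than Round 1 clients, so the window must be set separately for each round.

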Aim 1. The proposed intervention will focus and guide RWPA support-service providers in assisting their clients who are flagged on D2S reports as virally unsuppressed. The D2S reports will be generated based on Registry data on viral load (VL) test dates and values (and client vital status) and eSHARE (RWPA program) data on client activity in the recipient RWPA program. Reports will be delivered (through separate secured transfers to individual accounts for authorized recipients) in two rounds per implementation period, with the first round marking the start of that implementation period and the second round beginning halfway through the period. D2S reports will be generated at the DOHMH using existing data sources (surveillance and programmatic) that are already securely managed and routinely merged and analyzed at the DOHMH. In Period 1, D2S reports and capacity-building will be delivered to 13 of the 27 agencies (13 agencies randomized to early implementation), while D2S will be delivered to all 27 agencies in Period 2. Because of the odd number of agencies determined to have sufficient numbers of unsuppressed behavioral health and housing clients to be eligible for the trial at the time this project actually began in mid-2021, two agencies that had smaller numbers of trial-eligible clients were paired with one agency that had a larger number of trial-eligible clients (and was randomized to early implementation). Period 0 (baseline) data are available on all 27 agencies for retrospective report simulations and determination of TVS and time to VS, and between-site differences in those outcomes, among individuals found to be unsuppressed in the pre-intervention period.

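### The 12-week buffer in the secondary HCV analysis is keyed to the second negative test and the cure outcome has no closing date, so the rule does not do what it is stated to do

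*Combined protocol and SAP*

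**What the plan says.** All the HCV rules stand in one paragraph, Section K, Aim 1, HCV Cure Analysis Plan.

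- Treatment receipt: "HCV treatment receipt will be defined as a client's first negative HCV RNA Qualitative NAA test preceded by a positive RNA test".
- Cure: "HCV cure will be defined as two consecutive negative HCV RNA tests any time after the most recent positive HCV RNA test".
- Purpose of the 12-week buffer: "to avoid attributing to the reports HCV cures resulting from HCV treatment initiated prior to report distribution".
- Trigger of the buffer: "The 12-week buffer period applies if the 2nd negative RNA test was within the 12 weeks after reports were disseminated".
- Periods: "This analysis will include data from individuals in Period 0 and Period 1". A difference-in-difference comparison of Period 0 with Period 1 is optional.
- Methods: similar to those for viral suppression (VS). No follow-up window is named.

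Elsewhere, Section J (Aim 1) has 13 agencies receiving D2S in Period 1, "while D2S will be delivered to all 27 agencies in Period 2". Section K, Retrospective Analyses, puts "the start of each implementation period exactly 12 months after the start of the prior implementation period". That subsection gives TVS a six-month window. It restricts time to VS to clients flagged in Round 1 reports, with this reason: "To allow a full, discrete 12-month follow-up period, while avoiding contamination between intervention and control observations". In its retrospective simulation it also drops clients who were suppressed before a report could have been issued. Section G says the HCV data are added with the eligibility criteria left unchanged.

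**The concern.** The stated purpose of the buffer concerns when treatment began, but its trigger is the date of the second negative test. These are different events, and the same paragraph marks treatment by the first negative. The rule can therefore let through the cures it was written to remove.

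Three gaps add to this. Nothing removes cures completed before the report, because the buffer looks only at the 12 weeks after dissemination. No date closes the cure outcome. And the buffer starts at report dissemination, which no agency had in Period 0 and delayed agencies did not have in Period 1.

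At stake is whether the HCV comparison counts cures that D2S could have influenced, over comparable follow-up, by the same rule in all four cells (early or delayed agency, Period 0 or Period 1). If these rules are left open until analysis, there is also discretion over which cures count.

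**Working it through.** The plan gives no HCV sample size, event count, cure rate or power, so there is no figure to reproduce. The check is logic on test dates, plus illustrations on stated assumptions.

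**1. Which cures pass the buffer.** Let g be the weeks between the two consecutive negatives (assumed; not in the documents). Take a straddling cure, with the first negative U weeks before the report and the second g − U weeks after it. It passes when g − U > 12, that is, U < g − 12. With U uniform on (0, g), the share passing is (g − 12)/g for g above 12.

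| g (weeks) | Share of straddling cures that pass |
|---|---|
| 12 | 0/12 = 0% |
| 18 | 6/18 = 33% |
| 26 | 14/26 = 54% |

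Measured from treatment start, the same formula holds with T, the weeks from treatment start to second negative, in place of g: 0% at T = 12, 4/16 = 25% at 16, 12/24 = 50% at 24, and 24/36 = 67% at 36. The leak exists for any interval above 12 weeks. These are shares of straddling cures only; the documents do not show how many cures straddle.

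**2. Where follow-up can run.** Periods start 12 months apart.

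| Cell | If the Period 0/1 limit applies to test dates | If it only selects people |
|---|---|---|
| Period 0, early agency | Cures in Period 1, under D2S, not prevented | Same |
| Period 1, delayed agency | Follow-up stops before D2S | Cures in Period 2, under D2S, not prevented |

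The first row holds on either reading and affects the baseline cell of the optional difference-in-difference comparison.

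**3. Direction.** Assumed for illustration: new-cure probability 20% in control. A true OR of 2.0 then gives odds 2 × 0.25 = 0.5, or 33.3%, under D2S.

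- Equal carry-over c in both arms, p = c + (1 − c) × new-cure probability. At c = 10%: control 0.28, D2S 0.40, OR = (0.40/0.60)/(0.28/0.72) = 1.71. At c = 5% and 20% the OR is 1.83 and 1.56. The effect is diluted.
- A fraction f of control outcomes accrued under D2S. At f = 50%: control 0.5 × 0.20 + 0.5 × 0.333 = 0.267, OR = 0.50/0.364 = 1.38. At f = 25% and 75% the OR is 1.64 and 1.17. Again dilution.
- No true effect, with carry-over cures recoded as non-cures only where reports were issued. At c = 10%: control 0.28, D2S 0.9 × 0.20 = 0.18, OR = (0.18/0.82)/(0.28/0.72) = 0.56. At c = 5% and 20% the OR is 0.74 and 0.34. The bias is against D2S. This takes the buffer to catch every carry-over cure, so it is the extreme case.

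**The case against.** A reader might infer that control clients will be followed into D2S, or that every Period 0 early-agency client and every Period 1 delayed-agency client becomes exposed. The documents do not say so. The analysis is limited to Periods 0 and 1 and delayed agencies start in Period 2. If that limit applies to test dates, Period 1 controls are never followed into D2S. The open phrase in the cure definition can also be read as ordering the tests rather than setting follow-up length. Even with open follow-up, being listed on a report requires active enrollment and a qualifying status at that time (Section E). What stands is that the text does not prevent such follow-up.

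A reader might also infer that the buffer applies in the exposed arm only. The Section K Overview has Period 0 reports generated retrospectively and clients in both arms followed from report issue, and Retrospective Analyses shows how a simulated issue date is fixed. Mock dates are therefore available. What stands is that the HCV paragraph does not say they anchor the buffer.

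Finally, the leak might be taken to create a false D2S benefit. Agencies are randomized, so carry-over from earlier treatment is expected in both arms, and an equal leak mainly dilutes.

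The analysis is secondary and absent from the stated aims and the trial's power analysis. That limits the importance of the point. It does not answer it, because the buffer as written fails its own stated purpose.

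**Conclusion.** The point holds in a limited form. On the plan's own definitions, the buffer does not remove cures from treatment received before the report when the second negative falls in week 13 or later, and it does not exclude cures completed before the report. This needs no outside fact. Contamination of control follow-up and unequal buffering by arm are possibilities that the text leaves open; neither is written into the plan.

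The size cannot be determined. The 0%, 33% and 54% rest on assumed retest gaps and uniform timing, and the odds ratios on assumed cure and carry-over rates. The likely result is dilution if the leak is equal across arms, and bias against D2S if the buffer is used only where reports were issued. TVS and time to VS are untouched. The paragraph should be corrected before the HCV data are analysed.

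**What to change.** Rewrite the HCV paragraph as follows.

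- Index date: use one rule, the actual or mock report issue date, in all four site-period cells.
- Risk set: clients whose last HCV RNA before the index date is positive. First negatives and cures before the report then drop out in both arms, on baseline information only.
- Buffer: if the 12 weeks are kept, apply them to the first negative, identically in all cells. Count buffered events as non-events and keep those clients in the denominator. Excluding them would select on a post-report outcome that D2S may itself change.
- Window: count treatment receipt and cure within one fixed window that closes before the agency's next period starts.
- Rounds: use Round 1 index dates for cure, as the plan does for time to VS, so that 12 months are available. A Round 2 index date comes six months later and leaves about 52 − 26 = 26 weeks, or 14 after the buffer. With a gap of 18 or 26 weeks the second negative falls at week 12 + 18 = 30 or 12 + 26 = 38 at the earliest, too late for Round 2 but within Round 1's 52 weeks.

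Reconcile the new risk set with the Section G statement that eligibility criteria are unchanged.

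The registry data are the same, so the work is one paragraph plus a matching line in Section G. The price is fewer countable cures, no Round 2 contribution to the cure outcome, and the loss in every cell of any genuine response whose first negative falls inside the buffer.
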